4.2. Pre-inclusion / Pre-exclusion Criteria

The pre-inclusion/pre-exclusion criteria can be checked before informed consent is obtained since the process does not involve any study-specific procedures.

Pre-inclusion Criteria

- 15 years of age or older
- Male or female
- Able to ingest at least one complete meal per day (or at least one sachet of Plumpy'Nut®)*
- Karnofsky score > 50 (see Appendix 2 Karnofsky Performance Scale; p 90)
- Late-stage HAT due to *T.b. gambiense* with confirmed evidence of parasite in blood and/or lymph and/or CSF, certified by the report from the mobile team, with details on examinations performed and CSF WBC count, or performed at the investigational centre.

If testing for parasites in CSF is negative, a CSF WBC > $20/\mu$ L will be required to confirm late-stage HAT (54).*

 Having a permanent address and able to comply with the schedule of follow-up visits.

Pre-exclusion Criteria

- Severe malnutrition, defined as Body Mass Index < 16.
- Unable to take medication by the oral route.*
- Pregnancy or breast-feeding.
- Clinically significant medical condition that could, in the opinion of the Investigator, jeopardise the patient's safety or participation in the study, including, but not limited to significant liver or cardiovascular disease, suspected or proven active infection, CNS trauma or seizure disorder, coma or consciousness disturbances.
- Severely deteriorated general status, including as a result of cardiovascular shock, respiratory distress or end-stage disease.
- Any condition that affects the patient's ability to communicate with the Investigator as required to complete the study.

^{*} Criteria to be checked prior to randomisation.

- Any contraindication to imidazole drugs, i.e. known hypersensitivity to imidazoles, or to NECT, i.e. known hypersensitivity to effornithine.
- Prior treatment for HAT.
- Prior enrolment in the study.
- Foreseeable difficulty complying with follow-up, including migrant worker, refugee status, itinerant trader.
- History of alcohol or drug addiction.

4.3. Inclusion and Exclusion Criteria

Once the Investigator has checked that the patient fulfils the pre-inclusion/preexclusion criteria, s/he will invite the patient to participate in the study and initiate the process for collecting the patient's informed consent (see Section 14.2 Informed Consent Process; p 80). Treatment for any concurrent disease will be initiated, if necessary, and further investigations will be performed.

The inclusion and exclusion criteria will then be checked, just prior to randomisation. The pre-inclusion/pre-exclusion criteria marked with an asterisk (*) will be checked again before randomisation.

inclusion Criteria

• Signed informed consent form.

Exclusion Criteria

- Clinically significant laboratory test abnormality, including for example:
 - aspartate aminotransferase and/or alanine transferase more than 2 times the upper limit of normal (ULN)
 - total bilirubin more than 1.5 x ULN
 - severe leukopenia at < 2000/mm³
 - potassium (K+) < 3.5 mmol/L
- Pregnancy confirmed by a positive urine pregnancy test within 24 hours prior to the start of treatment (see Section 5.8.3 Contraception; p 41)
- Unstable abnormalities on ECG
- QTcF ≥ 450 msec, on automatic reading on two successive ECGs in resting position, performed 10 to 20 minutes apart
- Patients not tested for malaria and/or not having received appropriate treatment for malaria (see Section 5.8.1 Malaria; p Error! Bookmark not defined.).
- Patients not having received appropriate treatment for soil-transmitted helminthiasis (see Section 5.8.2 Helminthiasis; p Error! Bookmark not defined.)

The following criteria are considered to be temporary exclusion criteria

- Traumatic lumbar puncture, i.e. red blood cells visible in CSF; repeat lumbar puncture can be performed 48 hours later.
- Recovery period after treatment for malaria and/or treatment for helminthiasis, i.e. approximately 3 days.
- Abnormalities on laboratory tests or ECG that can be controlled within a few days after the initial assessment. If the value returns to normal or is not considered clinically significant, the patient can be included in the study.

Patients who fulfil the inclusion and exclusion criteria will be referred to as "included patients" and can be randomised.

Patients who are excluded will be treated in accordance with usual practice in the centre, and the reasons for exclusion from the study will be recorded.

5. Treatments

5.1. Investigational Product

Fexinidazole, 600 mg tablets, administered by the oral route after the main meal of the day, i.e. within 30 minutes after the start of the meal, in accordance with the following dosing regimen:

- 1800 mg (3 tablets) in a single daily intake for 4 days,
- followed by 1200 mg (2 tablets) in a single daily intake for 6 days.

The total duration of treatment will be 10 days.

Fexinidazole will be provided by DND*i*, [name].

5.2. Reference Treatment

Nifurtimox-Eflornithine Combination Therapy (NECT):

- Nifurtimox tablets, administered by the oral route three times daily, at the dose of 15 mg/kg/day, for 10 days.
- Eflornithine, administered twice daily as a 2-hour IV infusion, at the dose of 400 mg/kg/day, for 7 days.

NECT will be provided by DND*i*, [name].

5.3. Treatment Allocation

Patients will be randomised at a 2:1 ratio, with two patients in the fexinidazole group for 1 patient in the NECT group.

Each patient who fulfils the inclusion criteria will enter the randomisation process. Treatment will be allocated using a centralised internet-based system in order to avoid bias. After randomisation, the patient will be assigned to one of the two treatment groups, and the number of the treatment pack will be recorded in the patient's file and on the pharmacy log sheet (included in the pharmacy manual).

The patient will be considered to have completed his/her participation in the study once the last protocol-planned visit, i.e. the TOC visit at Month 18, has taken place. The visit at Month 24, at the end of the additional follow-up period, has been planned in order to comply with current recommendations in the National HAT Control Programmes.

5.4. Labelling and Packaging of Treatments

Fexinidazole tablets will be packaged in aluminium-aluminium blister packs. Each blister pack will contain the number of tablets necessary for one day of treatment, i.e. 3 tablets for the first 4 days, and 2 tablets for the next 6 days. The 10 blister packs will be packaged in an individual treatment pack for each patient.

NECT will be provided in its commercial packaging, i.e. one bottle containing 100 tablets of nifurtimox (Lampit®) per patient and 14 bottles of effornithine (Ornidyl®) per patient. The two products will be specially labelled for the study. The 15 bottles will be packaged in an individual treatment pack for each patient.

The material required for the sterile infusions will be packaged in separate packs.

The labelling of the secondary packaging will display the following information:

- Name of Sponsor*, name and contact details for the Coordinating or Principal Investigator
- Study number*
- Drug name* and dosage strength*
- Dosage form*, route of administration*, number of dosage units*
- Instructions for use
- Statements "For clinical study use only" and "Keep out of reach of children"
- Batch number* and treatment pack number*
- Expiry date and storage conditions

The information items marked with an asterisk (*) will also be displayed on the primary packaging of the study treatments.

Information on fexinidazole will be provided in the Investigator Brochure attached to the protocol submitted to the National Authorities. Information on NECT can be obtained from the product information for Ornidyl® and Lampit®.

5.5. Accountability of Treatments

The study treatments will be shipped to the coordinating study site, i.e. DND*i* Kinshasa for the DRC, or directly to the investigational centres.

Study-specific forms will be used for accountability of the study treatments. Appropriate records concerning receipt, use, returns, loss and any other disposition of the treatments will be maintained by the Investigators on site, or their delegates, under the supervision of the Principal Investigator. Study monitors will check accountability of the study treatments during on-site monitoring visits.

All study treatments must be stored in a locked room, or a locked cabinet if no specific room is available, at each investigational site, with access restricted to the nurse in charge of the pharmacy or to authorised study personnel.

The supplies of fexinidazole and NECT for the study must not be used for purposes other than the present protocol. The Investigator and the site staff may not, under any circumstances, provide other Investigators or healthcare services with the study treatments, or allow the treatments to be used other than as described in this protocol without prior written approval from DND*i*.

5.6. Storage of Treatments

Neither the IP nor the reference treatment requires shipping or storage under refrigerated conditions.

Eflornithine should be stored at room temperature prior to dilution in water for injections. Fexinidazole and nifurtimox should be stored at a temperature not exceeding 30°C. NECT is frequently stored in pharmacies in the rural setting that have no air conditioning. Long-term stability studies have shown that fexinidazole, stored in the bottle, remains stable at 30°C under conditions of high humidity.

Fexinidazole and nifurtimox must be protected from light. This condition is ensured by the fact that they are packaged in aluminium-aluminium blister packs and in amber-glass bottles.

The stability of the tablets in the aluminium-aluminium blister packs and amberglass bottles will be monitored in the context of regulatory stability studies.

The storage conditions, including the temperature, must be monitored by the study personnel and appropriate records should be available.

5.7. Blinding and Procedure for Unblinding

The study is being conducted using an open-label design because the route of administration and dosing regimen are different for the two study treatments. Thus, the patients and the Investigators will necessarily know which treatment is administered. Treatment compliance will, however, be recorded in the e-CRF in such a way that neither the Sponsor nor its representatives can identify the treatment administered.

- Persons involved in the study who are blinded to treatment received by the patient: the Sponsor, persons working on data management, the study statistician, the committee in charge of centralised reading of triplicate ECGs and the Data Safety Monitoring Board (DSMB). The latter may request lifting of the blind at any time upon written request;
- Persons not blinded to treatment: patients, Principal Investigators and their teams, monitors, independent statistician in charge of FAs, members of the Independent Steering Committee (ISC) at their request on a case-by-case basis, persons responsible for the interactive response system and persons working in Information Technology.

Data management will be carried out under blinded conditions. DND*i* personnel will not have access to information regarding which treatment was received or to detailed data on compliance, with the exception of the person in charge of Pharmacovigilance, if necessary.

The blind will be lifted for the independent statistician in charge of analysing the primary efficacy endpoint for the interim analysis.

If this analysis proves to be significant, the blind will then be lifted for:

- the statistician in charge of the study, who will validate the interim primary analysis and then proceed with all of the planned analyses in the interim analysis,
- the person in charge of preparing the clinical study report (CSR).

In that case, the study statistician and the person in charge of the CSR will no longer participate in decisions taken during data review for the subsequent analyses.

In addition, in order to maintain the blind among members of the Sponsor's team, the patient's initial code will not appear in individual data listings in the CSR. A new ID code will be assigned by the statistician. Only the person in charge of Pharmacovigilance for the Sponsor and the person in charge of the CSR will have access to the corresponding patient codes.

If the analysis of the primary efficacy endpoint for the interim analysis proves not to be significant, no other analyses will be performed and the blind will be maintained for the study statistician and the person in charge of preparing the CSR until the time of data review for the final analysis.

FAs will be performed by an unblinded independent statistician who is not involved in preparing the study, in the blind review of data or in the final statistical analyses. S/he will provide recommendations to the DSMB/ISC with regard to stopping the study for reasons of futility or to continuing the study. The magnitude of the treatment effect will not be revealed. If the study is allowed to continue, this will signify that efficacy is deemed sufficient from an ethical standpoint, but does

not inform about the study's chances of success. Indeed, the endpoints in the FAs are different from the primary endpoint: not only do the conditions for stopping the study differ from those that define treatment success, but the size of the sample in the FAs is small.

The logistic models will be validated in a fully blinded manner, regardless of the treatment group.

After the data base lock on the primary analysis (18 months data), the sponsor, the data management and the statistician will be unblinded. Once all patients reached their 24 months follow up, a sensitivity analysis could be performed on request.

5.8. Concomitant Treatment

5.8.1. Malaria

All patients will undergo a test to detect malaria. All patients with a positive thick smear and/or rapid diagnostic test (RDT) should receive treatment.

Prior to starting treatment for HAT, malaria will be treated with Coartem®, unless there are individual contraindications such as hypersensitivity to one of the components or severe malaria. All existing artemisinin-based combination therapies against malaria have effects on the QT interval. Coartem® was chosen because its effects on QT-interval prolongation are well known, moderate and well quantified (19). The choice was also made in order to minimise confounding factors regarding the assessment of fexinidazole-related QT-interval prolongation. The Sponsor will provide Coartem® free of charge.

In patients with a contraindication to Coartem®, the Investigator can choose another antimalarial agent. The choice must be documented.

Treatment for malaria will be followed by a recovery period of at least 3 days between the last dose of the antimalarial agent and the first administration of treatment for HAT, as per usual practice in the investigational centres.

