Study Schedule	 Screening: D-15 to D-1 Baseline assessment: D-4 to D-1 Randomisation: D-1 Treatment: D1 to D10 End of Treatment Visit: D11 End of hospitalisation Visit: D13 to D18 Observation Period: D1 to D18 (for safety) Additional Follow-up Visit: 9 weeks after D1 (D64 to D70) Follow-up Visits: M3 - M6 - M12 - M18 (Test of Cure) - M24 (Additional Follow-up Visit) after D11
Statistical	Populations
Analyses	The primary analysis will be performed on the Intention-to-Treat population.
	Sensitivity analyses will be performed on patients who completed the treatment, evaluable patients and the per protocol population.
	Interim Analysis
	An interim primary analysis for success will be performed on the first 195 randomised patients who have theoretically reached the 12-month follow-up visit and will exclude patients for whom no post-treatment data are available because the patient fled the area strictly for reasons of armed conflict. The analysis will be identical to the final primary analysis with the exception of the threshold for significance, the rule for imputing missing data (see Adjustment of Type-I Error for Multiplicity) and the assessment visit, which will be 12 months instead of 18 months.

A sensitivity analysis, including all randomised patients, will be performed and will consider all patients who fled for reasons of armed conflict as failures.

If the interim primary analysis for success should not prove to be significant, no further interim secondary or sensitivity analyses will be performed. If the analysis proves to be significant, all of the interim secondary and sensitivity analyses will be performed in accordance with the approach described for the final analyses, i.e. those initially planned. In addition, the success rate at 18 months will be compared, using a superiority test, to the historical success rate for melarsoprol at 18 months, i.e. 73.7%. No adjustment of the threshold for significance will be made in this analysis. The time course of the success rate, i.e. EOT, 6 months, 12 months and 18 months, will be studied using the Kaplan-Meier approach. The cumulative failure rate at each visit will be presented graphically including historical data for melarsoprol and effornithine.

The study will be continued to completion regardless of the result of the interim analysis, and all of the analyses planned in the protocol and SAP will be performed.

Primary Analysis

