18 months and 24	18 months ± 4 weeks 24 months ± 4 weeks	 Patient alive with no evidence of trypanosomes in any bodily fluid and CSF WBC ≤ 20/µL Patients with no signs of HAT and refusing to undergo 	 Any reason prompting the Investigator to request an additional follow-up visit 	 CSF WBC > 20/µL Neurological signs or symptoms leading to use of rescue treatment 	 Evidence of trypanosomes in any bodily fluid
24 months		lumbar puncture and who, in the opinion of the Investigator do not require rescue treatment or an additional follow-up visit			

An uncertain outcome may be a discrepancy between the clinical picture and the laboratory findings, or any situation that leads the Investigator and the study team to consider that an additional follow-up visit is required to decide whether or not to provide rescue treatment. This classification will not be used directly for statistical purposes.

6. Schedule of Study Procedures and Assessments6.1. Timing of Assessments

See Table 4 - Timing of Assessments (p 99)

- D-15 to D-1: Patient screening with detection of *T.b. gambiense*, pretreatment of concomitant malaria and/or helminthiasis, if any, ECG and laboratory screening tests
- D-4 to D-1: Baseline assessment
- D1 to D10: Treatment period
- D8 to D12: PK sampling for patients in the fexinidazole group
- D11: End-of-Treatment (EOT) visit
- between D13 and D18: End-of-Hospitalisation (EOH) visit; if hospitalisation is prolonged beyond D18, the EOH visit should be recorded on D18 and an unscheduled visit should take place at the actual time of discharge from hospital
- Additional Follow-up Visit: in Week 9 after D1, i.e. D64 to D70, for patients who reach this visit starting in mid-December 2014
- Follow-up Visits: at M3, M6, M12, M18 and M24 after D11, see Table 3 Theoretical Schedule of Visits and Acceptable Leeway). The timing of follow-up visits is calculated from D11 (EOT).

Theoretical schedule of visits	Ideal timing of visits	Acceptable leeway*	
End-of-Treatment visit (EOT)	D11 after the Start of Treatment (SOT) (D1 after EOT)	Between D11 and D12 after SOT (D1 or D2 after EOT)	
End-of-Hospitalisation visit (EOH)	Between D13 and D18 after SOT (D3 and D8 after EOT)	D18 at the latest	
Week 9 after D1	D64 to D70		
3 months	3 months ± 1 week after EOT	2-4 months after EOT	
6 months	6 months ± 2 weeks after EOT	5-9 months after EOT	
12 months	12 months ± 4 weeks after EOT	10-16 months after EOT	
18 months	18 months ± 4 weeks after EOT	17-21 months after EOT	

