6.2.3. Baseline Assessment

The following assessments will be performed before randomisation to assess the patient's baseline status just before the start of treatment. The assessments will also provide confirmation of the patient's eligibility to participate in the study, just before randomisation:

- Review of inclusion and exclusion criteria
- Vital signs, including body temperature, blood pressure and heart rate
- Verification of clinical signs and symptoms of HAT
- Physical and neurological examinations
- Collection of concomitant treatment
- Urine pregnancy test for women of child-bearing potential
- Laboratory safety assessments (see Appendix 3 Laboratory Tests; p 96)
 whenever possible, all laboratory tests will be performed on fasting patients:
 - Haemoglobin
 - Haematology: WBC, platelet count
 - Biochemistry: albumin (ALB), alkaline phosphatase (ALP), alanine aminotransferase (ALAT), aspartate aminotransferase (ASAT), blood urea nitrogen (BUN), chloride (CI-), creatinine (CRE), glucose

² Only patients at sites where PK sampling will take place.

(GLU), potassium (K+), sodium (Na+), calcium (Ca2+), total bilirubin (TBIL), bicarbonates (tCO₂) and total protein (TP)

- Urine analysis, i.e. WBC, pH, protein, urobilinogen, blood, nitrites, glucose, ketone bodies and bilirubin
- Digital ECG recording (CarTouch®): triplicate tracings to assess QT interval. The tracings will be uploaded to the e-CRF for specific analysis of QT interval.
- If the assessments mentioned in Section 6.2.2, i.e. haemoglobin, haematology, biochemistry and urine analysis, were performed within 4 days prior to the first administration, the findings will be considered as baseline values and the tests will not be repeated at the Baseline Assessment.

A treatment pack will be assigned to each randomised patient using the internetbased randomisation process accessible via the e-CRF. Patients will receive treatment over 10 days in the hospital/investigational centre.

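### The antimalarial recovery period is not tied to the baseline triplicate ECG, so a QT baseline 1 to 2 days after a QT-affecting drug is permitted

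*Protocol*

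**What the plan says.** Section 5.8.1 requires "a recovery period of at least 3 days between the last dose of the antimalarial agent and the first administration of treatment for HAT". The same section says that "All existing artemisinin-based combination therapies against malaria have effects on the QT interval", and explains the choice of antimalarial in part by QT: "The choice was also made in order to minimise confounding factors regarding the assessment of fexinidazole-related QT-interval prolongation".

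Section 4.3 lists as a temporary exclusion "Recovery period after treatment for malaria and/or treatment for helminthiasis, i.e. approximately 3 days". The criteria in that section are checked immediately before randomisation, and the study schedule in the Protocol Summary gives "Randomisation: D-1".

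The QT baseline is set elsewhere. Section 6.1 gives "D-4 to D-1: Baseline assessment". Section 6.2.3 places these assessments before randomisation, describes them as capturing the patient's "baseline status just before the start of treatment", and includes "triplicate tracings to assess QT interval. The tracings will be uploaded to the e-CRF for specific analysis of QT interval". Section 6.3.2 repeats the baseline triplicate for all patients. Table 4 marks malaria pretreatment, with its recovery period, in the screening column, which runs from D-15 to D-1. Section 9.10 lists QT/QTcF prolongation measured against baseline among the ECG analyses.

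**The concern.** The protocol recognises the antimalarial as a QT confounder, but attaches the waiting period to the first dose and to randomisation. The measurement that the drug can distort is the baseline triplicate tracing, and no section sets a minimum interval between the last antimalarial dose and that tracing.

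If some antimalarial effect remains at baseline and has faded by the on-treatment tracings, the baseline is too high and the change from it too small. For a drug under QT scrutiny that is the non-conservative direction. The analyses exposed are the within-arm change from baseline and its categories, in patients treated for malaria.

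The D4 readings are the most exposed. Under section 6.3.2 the fexinidazole arm has triplicates 4 and 23 hours after the D4 dose, whereas the NECT arm has no triplicate between baseline and D7. The D4 change therefore has no same-day comparator and is read mainly within arm.

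**Working it through.** The protocol states no figure to reproduce. The check is a count of days.

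**Inputs.** Recovery of at least 3 days to D1 (5.8.1). Recovery of about 3 days, checked before randomisation on D-1 (4.3, Protocol Summary). Baseline tracing on D-4, D-3, D-2 or D-1 (6.1, 6.2.3). Screening D-15 to D-1 (Table 4). There is no day 0, so D-1 to D1 is 1 day.

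**Latest permitted last dose.** Section 4.3 binds before 5.8.1 does, because it is checked on D-1.
- Strictest reading, 3 full days clear before D-1 (D-4, D-3 and D-2): last dose no later than D-5.
- Looser reading, a date difference of 3 days to D-1: last dose no later than D-4.

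**Gap = tracing day minus last-dose day, in days**

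| Last dose | Tracing D-4 | D-3 | D-2 | D-1 |
|---|---|---|---|---|
| D-4 (looser reading only) | 0 | 1 | 2 | 3 |
| D-5 | 1 | 2 | 3 | 4 |
| D-6 | 2 | 3 | 4 | 5 |
| D-7 | 3 | 4 | 5 | 6 |

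On the strictest reading, a gap under 3 days arises in three combinations: last dose D-5 with a tracing on D-4 or D-3, and last dose D-6 with a tracing on D-4. A last dose on D-7 or earlier leaves every baseline day clear. With last-dose days from D-15 to D-5 there are 11 x 4 = 44 permitted combinations, so 3 of 44 (6.8%) are short. On the looser reading it is 6 of 12 x 4 = 48 (12.5%). These counts show how narrow the opening is. They are not frequencies, since nothing in the protocol says how sites spread doses and tracings over the window.

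**Direction.** With a last dose on D-5, the D4 tracings come 5 + 3 = 8 days after it, against 1 or 2 days for the affected baseline. Any waning effect is therefore larger at baseline than on treatment, and the difference is understated.

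**Size.** Let r be the antimalarial effect left at the baseline tracing, net of what remains on treatment, and f the share of an arm's patients affected. The mean change is understated by r in those patients and by f x r in the arm. The protocol gives neither quantity. Assuming, for illustration only, r of 0 to 10 ms and f of 10% to 50%, the arm-level figure runs from 0.1 x 0 = 0 ms to 0.5 x 10 = 5 ms. Nothing in the protocol supports one part of that range over another.

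**Who can still be reached.** Table 7 shows 357 of 390 patients (91.5%) enrolled by Q4 2014, with 33 (8.5%) forecast for Q1 2015. The reference list of this version includes a 2016 publication of a phase III trial in first-stage disease, so enrolment was probably complete when this version was issued.

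**The case against.** The best reply is that the intended order is plain: treat malaria in screening, let the patient recover, take the baseline, randomise. Table 4 marks pretreatment only under screening, and section 6.2.3 places baseline close to the first dose and includes a review of eligibility, of which the recovery period is part. That shows intent, and a site following it and recording on D-1 would have a gap of 3 or 4 days in the latest-dose cases above. It does not close the opening, because the screening window runs to D-1 and overlaps the baseline window, and no minimum gap to the tracing is stated.

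A second reply is that harm is not shown. This stands. The protocol gives neither the size and duration of the residual effect nor the share of patients treated for malaria. The 3-day figure is the protocol's own recovery rule, described as usual practice, and nothing shows that QT effects persist at 1 to 2 days or have gone by day 3.

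A third is that section 9.10 sends ECG methods to a separate analysis plan. That is fair for the sensitivity analysis, which that plan may already contain. The timing of the tracing is a visit rule and belongs in the protocol.

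Two stronger readings are tempting. A reader might take 5.8.1 alone, allow a last dose on D-3, and conclude that every baseline day is too early and that a tracing could even precede the last dose. That ignores section 4.3, which applies before randomisation. A reader might also infer that the fexinidazole-NECT comparison in section 2.1.3 is biased. Baseline precedes randomisation, so carry-over is balanced between arms on average and cancels in a comparison of change.

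**Conclusion.** The point holds as a loose visit window that works against the aim stated in section 5.8.1. Even on the strictest reading, the protocol permits, without requiring, a QT baseline 1 to 2 days after the last antimalarial dose.

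The consequence is a possible understatement of within-arm QT/QTcF prolongation in malaria-treated patients whose last dose fell late in screening. It rests on two assumptions that the protocol can neither confirm nor exclude: that some effect remains 1 to 2 days after the last dose, and that it wanes before the on-treatment tracings. The bias may be zero. Absolute QT/QTcF values do not use the baseline, entry safety is not weakened, and the primary efficacy analysis is not touched. This is a cheap improvement, at the lowest level of severity.

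**What to change.** In sections 6.2.3 and 6.3.2 and in Table 4, require that in any patient given an antimalarial the baseline triplicate ECG be recorded at least 3 days after the last dose. Write the rule as the gap itself and not as a fixed D-1. A D-1 tracing meets it only if the last dose was on D-4 or earlier, while a patient whose last dose was on D-7 or earlier can be recorded on any baseline day. Leave the 450 msec eligibility reading as it is.

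For patients already enrolled, use the concomitant medication recorded from screening onwards (Table 4) to flag those whose baseline tracing fell less than 3 days after the last antimalarial dose. Repeat the change-from-baseline QT/QTcF analysis without them, as a sensitivity analysis in the separate ECG plan. This assumes that the date of the last dose was captured. The number flagged would also show how often the short gap occurred.

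The cost is slightly less scheduling freedom for sites and one extra analysis. No procedure is added. The timing rule can reach at most 33 patients and probably none, so the flag and the repeat analysis are the part that matters.
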